5.5.1 Pharmacokinetic Sample Analysis

Serum samples will be analyzed for nivolumab, ipilimumab, BMS-986016 (relatlimab), or daratumumab concentrations by a validated method. In addition, selected samples may be analyzed by an exploratory analytical method that measures nivolumab, ipilimumab, BMS-986016 (relatlimab), or daratumumab for technology exploration purposes; exploratory results will not be reported.

5.6 Biomarker Assessments

Peripheral blood and tumor tissue will be collected prior to therapy and at selected time points on treatment as outlined in the Biomarker Sampling Schedule in [Table 5.6.9-1](#), [Table 5.6.9-2](#), [Table 5.6.9-3](#), and [Table 5.6.9-4](#) unless restricted by local requirements. Detailed instructions of the obtaining, processing, labeling, handling, storage and shipment of specimens will be provided in a separate Procedure Manual at the time of study initiation.

5.6.1 Determination of Tumor's Viral Positivity

Confirmation of viral status will be required prior to study drug assignment for EBV gastric cancer and HPV SCCHN tumor types in the metastatic cohorts. Confirmation of viral status will also be required prior to study drug assignment for SCCHN subjects enrolled in the neoadjuvant cohort and Metastatic Combination Cohorts A and C. For SCCHN subjects in Cohort D and in all other tumor types, viral status will not be required prior to subject enrollment, but will be determined retrospectively if the viral status is not already known. Viral testing determined more than 35 days prior to first dose may be used. Viral status will be determined using an appropriately validated test as described below for each of the tumor types.

EBV Gastric: In situ hybridization EBV RNA (EBER) of FFPE sections. Testing for EBV positivity will be performed prior to study drug assignment using the EBER1 DNP probe from Ventana in a properly certified lab. Samples interpreted as (+) if nuclear staining of any intensity above the background in tumor cells, provided the negative internal controls (adjacent normal tissue) are negative.

HPV Head and Neck: HPV p-16 status should be assessed using the following criteria: p16 IHC should be done with anti-p16INK4a clone E6H4 from MTM labs (Roche). Interpretation as positive if > 70% strong and diffuse nuclear and cytoplasmic staining is specific to tumor cells; p-16 status will be reported as either p-16 positive or p-16 negative. If results acquired according to these criteria are not available, then a sample (tissue on microscopic slides, tissue block or a fresh tissue biopsy in formalin) should be sent to sponsor-contracted laboratory for analysis. HPV 16 in situ hybridization may also be performed retrospectively.

Polyomavirus MCC: Assessment of polyomavirus by IHC will be performed retrospectively at a sponsor-contracted laboratory if the polyomavirus status is unknown. If the polyomavirus status is known, please report this information on the provided case report form.

Cervical, vaginal, vulvar, anal canal and penile: HPV positivity is defined by FDA approved tests (Cobas HPV Test; Digene Hybrid Capture 2 High-Risk HPV DNA Test; Cervista™ HPV HR and Genfind™ DNA Extraction Kit; Cervista™ HPV 16/18; APTIMA® HPV Assay) or other well validated commercially available tests (such as Ventana Inform HPV ISH test) comprising in situ hybridization, real-time PCR, or immunohistochemistry (IHC). High-risk HPV positivity includes the following subtypes: 16, 18, 31, 33, 35, 39, 45, 51, 52, 56, 58, 59, 66, and 68. Virus testing will be performed retrospectively only if results from prior accepted testing are not available. If the HPV status is known please report this information on the provided case report form.

EBV Nasopharyngeal: In situ hybridization EBV RNA (EBER) of FFPE sections. Testing for EBV positivity will be performed using the EBER1 DNP probe from Ventana in a properly certified lab. Samples interpreted as (+) if nuclear staining of any intensity above the background in tumor cells, provided the negative internal controls (adjacent normal tissue) are negative.

Soluble Biomarkers: Soluble factors, such as cytokines, chemokines, soluble receptors, and antibodies to tumor antigens may be characterized and quantified by immunoassays in serum. Analyses may include, but not necessarily be limited to, soluble CD25, soluble PD-1, soluble

LAG-3, and CXCL-9. Collected serum samples may also be used for the assessment of tumor antigen-specific responses elicited following treatment with monotherapy to explore which antitumor antibodies are most associated with clinical response. Antibody levels to cancer test antigens will be assessed by multiplex assays and enzyme-linked immunosorbent assay (ELISA).

5.6.2 *Viral-related Assessments*

Quantification of EBV DNA by PCR, when appropriate, to correlate viral load to response. MHC tetramers assay may be used for analysis of virus-specific T cells. The seropositivity to viral oncoprotein antibodies and anti-viral antibodies may be examined in serum samples. PBMCs and/or lymphocytes isolated from tumors may be used in ELISPOT assays for T cell responses to viral antigens and/or epitope spreading.

5.6.3 *HLA Genotyping*

HLA typing of peripheral blood samples may be assessed by standard genotyping methods.

5.6.4 *Immunophenotyping*

The proportion of specific lymphocyte subsets and expression levels of T cell co-stimulatory and inhibitory markers in peripheral blood mononuclear cell (PBMC) preparations may be quantified by cytometry. Analyses may include, but not necessarily be limited to, the proportion of T, B, and NK cells, proportion of memory and effector T cell subsets, and expression levels of PD-1, PD-L1, PD-L2, ICOS, and Ki67. Whole blood samples will also be collected to quantify myeloid-derived suppressor cells (MDSC) before and after treatment.

5.6.5 *Ex Vivo Functional Assays*

To explore whether nivolumab may restore T cell activation and function, peripheral blood mononuclear cells (PBMCs) will be isolated and cryopreserved. Assays of the functional status of effector T cells may be performed, including but not limited to, assays for interferon-gamma (IFN- γ) and CD107.

5.6.6 *Peripheral Blood Gene Expression*

The expression level of genes and miRNA related to response to nivolumab as monotherapy or in combination with either ipilimumab, BMS-986016 (relatlimab), or daratumumab will be quantified by molecular methods such as nanostring, RNAseq, microarray, and/or quantitative reverse transcription polymerase chain reaction (RT-PCR) analysis of whole blood samples. Analysis may include, but not necessarily be limited to, genes associated with immune-related pathways, such as T cell activation and antigen processing and presentation.

5.6.7 *T Cell Repertoire Analysis*

Low diversity of the peripheral T cell compartment has been shown to correlate with poor overall survival in metastatic breast cancer.¹⁸⁷ A standing theory in immuno-oncology suggests a diverse and activated immune environment is better adept at eradicating tumor compared to a skewed repertoire of naïve and tolerized T cells. In order to explore whether a diverse T cell repertoire is predictive of response to therapy, next generation, high-throughput, DNA sequencing maybe

performed on DNA isolated from peripheral blood and tumor tissue to quantitate the composition of the T cell repertoire prior to and during monotherapy.

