In the United States, almost 4900 cases of vulvar cancer are diagnosed each year, with over 1000 of those women expected to die from the disease; for cervical cancer in the US there are 12,000 new cases of invasive cervical cancer and approximately 4000 cancer-related deaths occur each year.⁵⁶ HPV infection is associated with the development of cervical, vulvar, anal canal, and penile cancers.⁷⁵ HPV 16 and 18 are the most common subtypes for vulvar, anal canal, and penile cancers; HPV 16, 18, 33, 6 and 31 are the 5 most frequently observed HPV types for cervical cancer. Whereas cervical cancer HPV infection occurs in nearly 100% of patients⁷⁶, HPV associated squamous vulvar cancer affects younger women⁷⁷ and is a warty squamous cell compared to keratinizing or differentiated. Only 70% of cases are associated with HPV infection.⁷⁸

Treatment for vulvar or vaginal cancer is typically surgical resection, though chemoradiotherapy is another option.⁷⁹ The 5-year survival for vulvar cancer depends on spread of disease, Local 86%, Regional 54%, and Distant 16%.⁸⁰ Treatment of recurrent disease includes surgical reexcision or resection and platinum based chemotherapy for metastatic disease. Recurrences are more likely local compared to distant (5.7%) and the 5-year survival rate was 60% for perineal recurrences, 27% for inguinal and pelvic recurrences, 15% for distant recurrences, and 14% for multiple recurrences.⁸¹

Treatment for cervical cancer is typically surgery for Stages IA - IIA1 and concurrent chemoradiation for Stages IB2 to IVA. The 5-year survival rate for cervical cancer depends on stage: IA 93%, IB 80%, IIA 63%, IIB 58%, IIIA 35%, IIIB 32%, IVA 16%, and IVB 15%.⁸² Treatment of recurrent disease is typically with surgery for resectable disease or chemotherapy plus bevacizumab, which improved ORR (48% vs 36%) and mOS (17 vs 13.3 months) compared to chemotherapy alone.⁸³ After first line chemotherapy, there is no standard of care that has demonstrated improved benefit over best supportive care.

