 - ii. Histologically confirmed HPV positive subjects progressing while on or after therapy with anti-PD-1 or anti-PD-L1 antibody as most recent therapy, defined as Squamous Cell Carcinoma of the Head and Neck (oral cavity, pharynx, larynx) not amenable to local therapy with curative intent (surgery or radiation therapy with or without chemotherapy). **(Combo C only)**
 - i. Cannot have had therapy discontinued due to serious and/or life-threatening anti-PD-1; anti-PD-L1 or anti-CTLA-4 antibody-related toxicity (e.g., dose-limiting toxicity in prior study) per Investigator's assessment in consultation with the BMS Medical Monitor.
 - ii. Last dose of antibody therapy must have been received \geq 30 days of first dose of study medication
 - iii. Cannot have had prior exposure to other IOs, such as, but not limited to, anti-CTLA-4 anti-PD-L2, anti-KIR, anti-CD137, or anti OX40 antibodies.
 - iv. anti-PD-1/PD-L1/CTLA-4 does not need to be considered a 1 of the previous lines of therapy.
 - (3) Histologically confirmed cervical, vulvar, or vaginal cancer, as defined above. If the viral results are known prior to enrollment, and they are viral negative, the patient would be ineligible.
 - (4) Histologically confirmed Merkel Cell Carcinoma
 - a. Subjects with no prior systemic treatment will be allowed to enroll

(5) Histologically confirmed Nasopharyngeal Carcinoma, as defined above. If the viral results are known prior to enrollment, and they are viral negative, the patient would be ineligible.

- HPV associated NPC is excluded in this cohort
- Keratinizing squamous cell carcinoma (WHO Type I) is excluded in this cohort due to the low prevalence of EBV infection in this population.

(6) Histologically confirmed anal canal or penile carcinoma. If the viral results are known prior to enrollment, and they are viral negative, the patient would be ineligible. (Metastatic Combination Cohorts only).

v) Recurrent/metastatic SCC of the cervix subjects not amenable to curative treatment with surgery and/or radiation therapy who are unsuitable for platinum-based therapy (ie, creatinine clearance of less than 60 mL/min or have experienced toxicity from prior platinum-based therapy) may enroll in the cervical cancer Combination B expansion cohort.

d) For both neoadjuvant and metastatic (monotherapy and combination)cohorts

- Eastern Cooperative Oncology Group (ECOG) performance status of 0 or 1
- Men and women of age 18 or older.

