7.9.2 Virus Status

- The following virus status subgroups will be considered by tumor type for cohorts (N-3) GYN (Cervical, vaginal, and vulva) Carcinoma, (N-4) Merkel Cell Carcinoma, (M-3) GYN (Cervical, vaginal, and vulva) Carcinoma, (MC-2a, MC-2b, MC-exp) Cervical Carcinoma, (MC-3a, MC-3b) anogenital HPV associated tumors (vaginal/vulvar/anal canal/penile), (M-4, MC-4a) Merkel Cell Carcinoma and (M-5, MC-5a) Nasopharyngeal Carcinoma (NPC), for which the virus status are tested retrospectively. .
- Virus status tested
 - Virus positive

- Virus negative
- Virus status not tested

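### HPV positivity spans 14 types, yet a 16/18-only assay is accepted without condition, so its negative can exclude or mislabel a tumor that meets the protocol's own definition

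*Protocol*

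**What the plan says.** Protocol 5.6.1 sets the rule for these five tumor sites: "Cervical, vaginal, vulvar, anal canal and penile: HPV positivity is defined by FDA approved tests", followed by named products. One is a separate entry for types 16 and 18: "Cervista™ HPV 16/18; APTIMA® HPV Assay) or other well validated commercially available tests". Nothing requires it to be paired with a broader test. The same paragraph then gives the type list: "High-risk HPV positivity includes the following subtypes: 16, 18, 31, 33, 35, 39, 45, 51, 52, 56, 58, 59, 66, and 68". The Synopsis and Protocol 3.3.1 carry the same tests and types.

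On retesting, 5.6.1 says: "Virus testing will be performed retrospectively only if results from prior accepted testing are not available". Its opening paragraph says much the same for these tumor types: status "will be determined retrospectively if the viral status is not already known".

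A negative has two consequences.

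- **Eligibility.** For metastatic cervical, vulvar and vaginal cancer, and again for anal canal and penile cancer, Protocol 3.3.1 says: "If the viral results are known prior to enrollment, and they are viral negative, the patient would be ineligible". The neoadjuvant criteria for cervical, vulvar and vaginal cancer contain no such exclusion.
- **Analysis.** SAP 7.5.1.2 splits ORR by virus positive and negative in the metastatic gynecological, cervical and anogenital cohorts. SAP 7.9.2 and 7.9.2.1 summarize BOR, PFS, OS, DOR and pCR by virus status. They include neoadjuvant cohort N-3 and describe these cohorts as ones "for which the virus status are tested retrospectively". SAP 7.9.2 has a category for status not tested. The SAP has no rule on which assay can support a negative.

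**The concern.** The definition and the accepted tests do not match. A positive 16/18 result satisfies the definition. A negative one says nothing about the other 12 listed types, yet the text gives it the same standing as a negative from a test covering them all, and the retest rule then leaves it in place.

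The protocol itself shows that the gap matters in this disease. Section 1.1.1.2 says "HPV 16, 18, 33, 6 and 31 are the 5 most frequently observed HPV types for cervical cancer". Types 31 and 33 are in the 14-type list and outside the range of a 16/18 assay.

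Two things are at stake: who may enter the metastatic cohorts, and whether the subjects reported as virus-negative in the descriptive summaries are negative by the protocol's definition.

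**Working it through.** The plan has no figure of its own on this point. The check is a trace through the text, followed by an illustration of size.

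**Step 1: the mismatch.** 14 types are listed. Removing 16 and 18 leaves 14 − 2 = 12. That the assay covers only 16 and 18 is read from the name the protocol gives it; the documents state no assay coverage.

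**Step 2: what happens to a tumor carrying only type 31 or 33 and tested only with the 16/18 assay.**

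| Situation | Rule that applies | Result |
|---|---|---|
| Metastatic, result known before enrollment | 3.3.1 known-negative rule | Ineligible, so never in any analysis |
| Neoadjuvant N-3, result known before enrollment | No viral exclusion in 3.3.1; no retest under 5.6.1 | Enrolled and carried as negative into SAP 7.9.2 |
| Metastatic, assay used for status set after enrollment | Permitted by the 5.6.1 test list | Negative in SAP 7.5.1.2 and 7.9.2 |
| No prior result, broader test used in the study | 5.6.1 retrospective testing | Correctly positive |

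The first two rows follow from a prior result. The third needs a separate event: a 16/18-only assay chosen for testing after enrollment. The text permits that, but nothing suggests it is planned.

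**Step 3: size of the exclusion.** Let u be the share of otherwise eligible HPV-positive patients whose only prior result comes from a 16/18-only assay. Let q be the share of HPV-positive tumors carrying only other listed types. Neither is in the documents, so both are assumed, and taken as independent.

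Wrongly excluded share = u × q:

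- u = 10%, q = 20%: 0.10 × 0.20 = 2%
- u = 25%, q = 30%: 0.25 × 0.30 = 7.5%
- u = 50%, q = 40%: 0.50 × 0.40 = 20%

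**Step 4: size in N-3.** Protocol 8.1 plans 21 evaluable subjects. If all 21 were HPV-positive, which is an upper bound, the same products give 21 × 0.02 = 0.4, 21 × 0.075 = 1.6 and 21 × 0.20 = 4.2 subjects mislabelled.

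**Step 5: how much a 16/18-only negative says.** With π the HPV prevalence and an assay that is perfect for 16 and 18, the share of its negatives that are truly positive is πq / (πq + 1 − π). This does not depend on u. It treats the protocol's HPV prevalence as prevalence of the 14 listed types.

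- Cervical: Protocol 1.1.1.2 says nearly 100%; π is taken as 98%. With q = 10%, 0.098 / (0.098 + 0.02) = 83%. With q = 40%, 0.392 / (0.392 + 0.02) = 95%.
- Vulvar: the same section gives 70%. With q = 10%, 0.07 / (0.07 + 0.30) = 19%. With q = 40%, 0.28 / (0.28 + 0.30) = 48%.

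In cervical cancer, then, most 16/18-only negatives would be false across this range of q, however few there are.

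**The case against.** The strongest reply is that the protocol says positivity is defined by these tests; it does not say that a 16/18 negative establishes a viral negative. A careful site could treat such a result as status not established and let retrospective testing apply. No sentence says outright that the assay stands alone or that its negative is never repeated. Sample handling is also referred to a laboratory manual that is not part of these documents.

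That reading is sensible, but the text does not direct anyone to it. The assay is listed on equal terms with the others, study testing is confined to cases without an accepted prior result, and a known negative is disqualifying. Two sites could follow the same words to different results. If the careful reading is intended, it still needs to be written down.

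Other parts of the reply stand in full:

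- Viral screening is not required before entry for these tumors (Protocol 3.1.1), so exclusion arises only where a prior result happens to exist.
- A reader might infer that false negatives would fill the virus-negative group of the roughly 110 cervical Combo B subjects. The prior-result route does not lead there, because those patients are excluded. It would take assumed use of the assay after enrollment, and the documents give no sign of how often that occurs.
- A reader might infer that a central comparison of virus-positive with virus-negative tumors is biased. None is planned for these tumor types. The trial is non-comparative, the objectives in Protocol 1.3 contain no such contrast for them, and the SAP summaries by virus status are descriptive.
- A reader might count HPV 6 as a missed type because 1.1.1.2 calls it frequent. It is not among the 14, so only 31 and 33 support the point.

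**Conclusion.** The text is wrong as written, at minor severity. Following it exactly can turn a tumor that meets the protocol's own definition into a negative. In the metastatic cervical, vaginal, vulvar, anal canal and penile cohorts, a prior negative of this kind costs the patient eligibility. In N-3, or where such an assay sets status after enrollment, it puts the subject in the wrong group of the SAP 7.9.2 summaries and, for the metastatic cohorts, of the SAP 7.5.1.2 ORR subgroups.

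The primary ORR uses all treated subjects, so its calculation does not change, and no sample-size figure depends on virus status. SCCHN is untouched, because it uses p16 staining.

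The size cannot be fixed from the documents. The exclusion figure of 2% to 20% is conditional on the assumed u and q and spans a factor of ten; it is a range, not an estimate. The conclusion also rests on reading the assay's coverage from its name.

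**What to change.** In Protocol 3.3.1 and 5.6.1 (and the Synopsis), state that a 16/18-only result is evidence of positivity only. A 16/18-only negative should count as status not available, both for eligibility and for the retest rule. The existing retrospective testing then applies to the baseline tissue that 5.6.9 already makes mandatory. Table 5.1-1 asks for a fresh tumor-cell collection when HPV status is missing, so the added sentence should say whether tissue already submitted is enough.

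In SAP 7.5.1.2 and 7.9.2, class a 16/18-only negative without a broader test as virus status not tested. That category already exists in 7.9.2; 7.5.1.2 lists only positive and negative and would need it added. Recording the assay used with each result makes the rule workable.

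The cost is a sentence or two in each document, a few retrospective tests, and slightly smaller virus-negative subgroups. Where enrollment is already closed, as in the anogenital combination cohorts since Revised Protocol 06, only the retest and the SAP classification can still help.

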5.6.8 Single Nucleotide Polymorphism (SNP) Analysis

In order to identify potential polymorphisms associated with safety and efficacy of nivolumab, selected genes may be evaluated for single nucleotide polymorphisms (SNP). Analysis may include but will not be limited to sequence polymorphisms linked to genes associated with the PD-1/PD-L1 pathway and activated T cell phenotype, including PD-1, PD-L1, PD-L2, and CTLA-4. A blood sample will be obtained at Day 1, unless restricted by local regulations.

5.6.9 Tumor Samples

Tumor tissue specimen requirements for the Neoadjuvant Cohort are as follows:

- At Baseline (Prior to first dose of study drug): Biopsy and submission of fresh tumor tissue is mandatory for all subjects. Biopsy is indicated for subjects with accessible lesions where biopsy is deemed safe by the Investigator.
- Day 29 (On-treatment) fresh samples obtained via scheduled surgical resection or scheduled biopsy are mandatory.
- Day 29 (On-treatment) samples must be reviewed by pathologist and a copy of the pathology report must be sent to BMS
- All other time points where tumor tissue collections are indicated, aside from baseline and Day 29, are described in [Table 5.6.9-1](#).

Tumor tissue specimen requirements for the Metastatic Cohort (Monotherapy and Combination Therapy) are as follows:

- At Baseline (Prior to first dose of study drug): Biopsy and submission of fresh tumor tissue, or submission of archived tumor tissue, is mandatory for all subjects. Biopsy is indicated for subjects with accessible lesions where biopsy is deemed safe by the Investigator.
- An on-treatment biopsy and submission of fresh tumor tissue is mandatory for subjects in each tumor type in the metastatic cohort to ensure an adequate number of paired samples to perform meaningful analyses to support biomarker objectives. Subjects with accessible lesions where biopsy is deemed safe by the Investigator should undergo biopsy per protocol.
- All other time points where tumor tissue collections are indicated, aside from baseline and the one mandatory on-treatment biopsy, are described in [Table 5.6.9-2](#) and [Table 5.6.9-3](#).

Tumor tissue specimen requirements for Subjects Treated with Study Drug Post-Standard of Care are as follows:

- At Cycle 1 Day 1 biopsy and submission of fresh tumor tissue is strongly encouraged for subjects with accessible lesions where biopsy is deemed safe by the Investigator.
- All other time points where tumor tissue collections are indicated, aside from Cycle 1 Day 1, are described in [Table 5.6.9-4](#).

Submission of fresh tumor tissue collected via biopsy is required for TILs isolation for ex-vivo functional assays (RPMI media preparation), and also for gene expression profiling (RNALater samples). Please refer to Central Lab Manual for detailed sample requirements.

Submission of tissue samples (FFPE tumor tissue block or slides) is required for characterization of tumor infiltrating lymphocytes (TILs) and tumor, utilizing immunohistochemistry (IHC) methods. A minimum of 1 FFPE tumor tissue block (preferred) OR minimum of 15 FFPE unstained sections are required for this purpose. Tissue for this purpose may be obtained during the screening phase, prior to resection, or collected as a standard of care procedure within 90 days prior to obtaining informed consent, and is mandatory. Please refer to Central Lab Manual for detailed sample requirements.

Tissue for protocol purposes should be obtained via excision, incision or core needle. Fine needle aspirates are prohibited.

Tumor samples obtained from bone metastases are not considered acceptable for PD-L1 testing because the PD-L1 assay does not include a decalcification step. For any cases where the only tumor tissue available is from a bone metastasis lesion, please discuss further with the study Medical Monitor.

All subjects may volunteer to undergo tumor biopsies at any time during therapy, if clinically indicated. When tumor biopsy is performed during these times, submission of tumor biopsy is strongly encouraged.

All tumor tissue sample submission upon progression is optional, and can be taken within 7 days at the discretion of the investigator.

Tumor-Based Biomarker Measures

Tumor biopsy specimens will be obtained from consenting subjects prior to administration of study drug to characterize immune cell populations and expression of selected tumor markers. Tumor biopsy collection and submission is mandatory for subjects with accessible lesions prior to therapy. Tumor tissue (obtained during the screening phase or collected as a standard of care procedure within 90 days prior to obtaining informed consent) will be provided for biomarker analysis if accessible and deemed safe by the investigator. For subjects where tumor tissue cannot be provided due to issues related to safety, the reason must be clearly documented in the medical record AND the BMS Medical Monitor must be contacted. Archival tissue should be submitted for these subjects. Submission of archival tissue is also encouraged for all subjects, irrespective of whether fresh biopsy tissue is available.

For cases when a complete response occurs, and an on-treatment biopsy is required but not feasible, these cases must be clearly documented in the medical record AND the BMS Medical Monitor must be contacted.

A tumor biopsy sample of subjects that have confirmed progression is optional, but strongly encouraged for the purposes of understanding mechanisms of resistance to therapy.

Biopsy samples may be used for the following assessments:

Characterization of tumor infiltrating lymphocytes (TILs) and tumor. Immunohistochemistry (IHC) will be used to assess the number and composition of immune infiltrates in order to define the immune cell subsets present within formalin-fixed, paraffin-embedded (FFPE) tumor tissue before and after exposure to therapy. These IHC analyses may include, but not necessarily be limited to, the following markers: PD-L1, PD-L2, PD-1, LAG3, IDO, GITR, T cell and macrophage markers. For the neo-adjuvant arm only TILs may also be assessed in fresh baseline biopsies and surgical resections by cytometry. Analysis of cytokines including but not limited to IFN- γ , IL-4, IL-13, IL-10, IL-17, and IL-32 γ may be done with multiplex qRT-PCR and/or amplified in situ hybridization (ISH) using fixed tumor tissue.

Tumor genotyping, mutational analysis, and tumor antigen profiling

RNA and DNA from tumor samples may be analyzed using whole-exome and transcriptome sequencing or another technology to determine the number of mutations found within a given sample relative to a normal host tissue, such as adjacent non-transformed cells or PBMC. Mutations that are detected will be analyzed for their ability to bind the MHC I and MHC II proteins using prediction algorithms. Evaluating the ability of tumor mutations to bind MHC molecules will provide evidence that these mutations are serving as antigens that are recognized by the immune system and are potential rejection antigens.

In addition to viral positivity, chromosomal translocations, aberrant expressions, and epigenetic modifications within tumor cells may be characterized and explored by IHC and RNA/DNA analysis of tumor biopsies. Associations of altered tumor cell genetic structure with nivolumab efficacy will be performed. This includes, but is not limited to, assessments of 9p24 copy number alterations.

Characterization of T cell repertoire. As described above, DNA sequencing may be performed on pre- and post-treatment tumor tissue to assess the composition of the T cell repertoire. DNA may be isolated from either the FFPE tumor block or from RNAlater, or equivalent preparations.

Gene expression profiling. Tumor biopsies that are collected in RNAlater or equivalent fixative maybe examined for mRNA and miRNA gene expression by nanostring, RNAseq, microarray, and/or quantitative real-time polymerase chain reaction (qPCR) to detect expression of selected immune related genes and regulatory pathways.

Ex vivo Functional Assays. To explore whether nivolumab may restore T cell activation and function, Tumor infiltrating Lymphocytes (TILs) will be isolated. Assays for phenotypic characteristic as well as functional status of effector T cells may be performed, including but not limited to, flow cytometry and peptide restimulation.

Table 5.6.9-1: CA209358 Biomarker Sampling Schedule (Neo-Adjuvant Cohort)

| Collection Time ^a | Serum | Plasma | PBMC (US and European Sites Only) | | Tumor Biopsy | Whole Blood | | |
|--|--------------|-------------------|-----------------------------------|--------------------|---------------------------|-----------------|--------------|-----|
| | Study Day | Soluble Biomarker | | Immuno-phenotyping | Ex-vivo Functional | Gene Expression | MDSC | SNP |
| Screening | | | | | | X ^b | | |
| Cycle 1 Day 1 | X | X | X | X | | X | X | X |
| Cycle 2 Day 1 | X | | X | | | X | | |
| Prior to Resection (Day 29) | X | | X | X | X ^c | X | | |
| CR Evaluation ^c | X | | X | | X (optional) ^c | X | | |
| During Treatment (when clinically indicated) | | | | | X ^c | | | |
| Upon Progression ^d | X (optional) | | X (optional) | X (optional) | X (optional) | X (optional) | X (optional) | |

^a Serum, PBMC, Plasma, and Whole Blood samples may be obtained \pm 3 days of the indicated time except for Cycle 1 Day 1 samples which must be collected prior to treatment.

^b Submission of fresh tumor tissue collected via biopsy is required for TILs isolation for ex-vivo functional assays (RPMI media preparation), and also for gene expression profiling (RNALater samples).

Submission of tissue samples (FFPE tumor tissue block or slides) is required for characterization of tumor infiltrating lymphocytes (TILs) and tumor, utilizing immunohistochemistry (IHC) methods. Tissue for this purpose may be obtained during the screening phase, prior to resection, or collected as a standard of care procedure within 90 days prior to obtaining informed consent, and is mandatory.

^c Fresh tumor tissue is required to be collected on Day 29. Day 29 tumor biopsy may be collected \pm 7 days. Day 29 biopsy must be reviewed by pathologist and the pathology report must be sent to BMS.

^d All sample submission upon progression is optional and can be taken at any time after progression at the discretion of the investigator.

Table 5.6.9-2: CA209358 Biomarker Sampling Schedule (Metastatic Monotherapy Cohorts and Metastatic Cohort Combo A and B)

| Collection Time ^a | Serum | Plasma | PBMC (US and European Sites Only) | | Tumor Biopsy | Whole Blood | | |
|---|-----------------------------|--------|-----------------------------------|--------------------|-----------------------------|-----------------------------|--------------|-----|
| | Soluble Biomarker | | Immuno-phenotyping | Ex-vivo Functional | | Gene Expression | MDSC | SNP |
| Study Day | | | | | | | | |
| Screening | | | | | X ^b | | | |
| Week 1 Day 1 | X | X | X | X | | X | X | X |
| Week 3 Day 1 | Mono & Combo A ^c | | Mono & Combo A ^c | | | Mono & Combo A ^c | | |
| Week 4 Day 1 | Combo B Only ^d | | Combo B Only ^d | | Combo B Only | Combo B Only ^d | | |
| Week 5 Day 1 | Mono & Combo A ^c | | Mono & Combo A ^c | | Combo A only X ^b | | | |
| Week 7 Day 1 | X | | X | X | | X | X | |
| Week 19 Day 1 | Combo A Only | | Combo A Only | Combo A Only | | Combo A Only | | |
| CR Evaluation | X | | X | | X (optional) ^e | X | | |
| During Treatment (when clinically indicated) ^e | | | | | X ^e | | | |
| Upon Progression ^f | X (optional) | | X (optional) | X (optional) | X (optional) | X (optional) | X (optional) | |

^a Serum, PBMC, Plasma, and whole blood samples may be obtained \pm 3 days of the indicated time except for Cycle 1 Day 1 samples which must be collected prior to treatment.

^b Submission of fresh tumor tissue is required for gene expression profiling (RNALater samples).

^c For Monotherapy, and Combo A; excludes Combo B

^d For cervical cancer and anogenital HPV associated tumors (vulvar/vaginal/anal canal/penile) only

^e All subjects may volunteer to undergo tumor biopsies at any time during therapy if clinically indicated. When tumor biopsy is performed, submission of tumor biopsy is strongly encouraged.

^f All sample submission upon progression is optional and can be taken at any time after progression at the discretion of the investigator. Submission of tissue samples (FFPE tumor tissue block or slides) is required for characterization of tumor infiltrating lymphocytes (TILs) and tumor, utilizing immunohistochemistry (IHC) methods. Tissue for this purpose may be obtained during the screening phase, prior to resection, or collected as a standard of care procedure within 90 days prior to obtaining informed consent. On-treatment tumor biopsies are mandatory. On-treatment tumor biopsy may be collected +/- 7 days.

Table 5.6.9-3: CA209358 Biomarker Sampling Schedule (Metastatic Combination Cohort Combo C and Combo D)

| Collection Time ^a | Serum | Plasma | PBMC (US and European Sites Only) | | Tumor Biopsy | Whole Blood | | |
|--|-------------------|--------|-----------------------------------|--------------------|---------------------------|-----------------|--------------|-----|
| | Soluble Biomarker | | Immuno-phenotyping | Ex-vivo Functional | | Gene Expression | MDSC | SNP |
| Study Day | | | | | | | | |
| Screening | | | | | X ^b | | | |
| Week 1 Day 1 | X | X | X | X | | X | X | X |
| Week 5 Day 1 | X | | X | | X ^b | | | |
| Week 9 Day 1 | X | | X | X | | X | X | |
| CR Evaluation | X | | X | | X (optional) ^c | X | | |
| During Treatment (when clinically indicated) | | | | | X ^c | | | |
| Upon Progression ^d | X (optional) | | X (optional) | X (optional) | X (optional) | X (optional) | X (optional) | |
| Upon Drug-Related AE • ≥ Grade 2 drug related neurological AE | X | | X | X | | | | |

^a Serum, PBMC, plasma, and whole blood samples may be obtained ± 3 days of the indicated time except for Cycle 1 Day 1 samples which must be collected prior to treatment.

^b Submission of fresh tumor tissue is required for gene expression profiling (RNALater samples).

^c All subjects may volunteer to undergo tumor biopsies at any time during therapy if clinically indicated. When tumor biopsy is performed, submission of tumor biopsy is strongly encouraged.

^d All sample submission upon progression is optional and can be taken at any time after progression at the discretion of the investigator.

Submission of tissue samples (FFPE tumor tissue block or slides) is required for characterization of tumor infiltrating lymphocytes (TILs) and tumor, utilizing immunohistochemistry (IHC) methods. Tissue for this purpose may be obtained during the screening phase, prior to resection, or collected as a standard of care procedure within 90 days prior to obtaining informed consent. On-treatment tumor biopsies are mandatory. On-treatment tumor biopsy may be collected +/- 7 days

Table 5.6.9-4: CA209358 Biomarker Sampling Schedule (Subjects Treated with Study Drug Post-Standard of Care)

| Collection Time ^a | Serum | PBMC (US and European Sites Only) | | Tumor Biopsy | Whole Blood | |
|---|--------------|-----------------------------------|--------------------|---------------------------|--------------------|-----------------|
| | | Soluble Biomarker | Immuno-phenotyping | | Ex-vivo Functional | Gene Expression |
| Cycle 1 Day 1 | X | X | X | X ^b | X | X |
| Cycle 2 Day 1 | X | X | | | X | |
| Cycle 3 Day 1 | X | X | | | | |
| Cycle 4 Day 1 | X | X | X | | X | X |
| CR Evaluation | X | X | | X (optional) ^c | X | |
| During Treatment (when clinically indicated) ^c | | | | X ^c | | |
| Upon Progression ^d | X (optional) | X (optional) | X (optional) | X (optional) | X (optional) | X (optional) |

^a Serum, PBMC and whole blood samples may be obtained \pm 3 days of the indicated time except for Cycle 1 Day 1 samples which must be collected prior to treatment.

^b Submission of tumor tissue is strongly encouraged, if feasible.

^c All subjects may volunteer to undergo tumor biopsies at any time during therapy if clinically indicated. When tumor biopsy is performed, submission of tumor biopsy is strongly encouraged.

^d All sample submission upon progression is optional and can be taken at any point after progression at the discretion of the investigator.

